## **9 CONTENT OF REPORTS**

The complete list of analyses contributing to the clinical study report is given in the Data Presentation Plan.

## **APPENDIX 1      ADVERSE EVENTS OF INTEREST DEFINITION AND CONVENTIONS**

The adverse events of interest including IMAE, select AE, and other event of special interest consist of a list of preferred terms grouped by specific category and by subcategory. These categories and subcategories are defined by the Sponsor and the list that is most current at the time of analysis will be used. Also changes may be made to this list with each new version of MedDRA.

### **Time-to onset definition**

Time-to onset of AE (any grade) for a specific category (e.g. pulmonary events, gastrointestinal events, ...) is defined as the time between the day of the first dose of study treatment and the onset date of the earliest AE (of any grade) in this category.

If the subject did not experience an AE (of any grade) in the category, time-to onset will be censored at the maximum follow-up time of all subjects in their respective treatment group (i.e for subjects without an event, follow-up time is defined from first dosing date up to last dosing date +30 days (or 100 days depending on the analysis) if subjects are off treatment and followed for at least 30 days (or 100 days depending on the analysis) , otherwise it is defined up to the last known alive date). The resulting Kaplan-Meier plot will represent the cumulative rate of the select AE (any grade) in the category over time.

Time-to onset of AE (grade 3-5) for a specific category is defined similarly but restricted to grade 3-5 AEs.

Time-to onset of drug-related (grade 3-5 or any grade) AE for a specific category is defined similarly but restricted to drug-related AEs.

Time-to onset for a specific subcategory is defined similarly but restricted to event of this subcategory.

### **Time-to resolution definition**

In order to derive the time-to resolution, overlapping or contiguous AEs within a specific category will be collapsed into what will be termed “clustered” AEs. For example, if a subject (without pre-treatment AE) experienced an AE from 1st to 5th January, another AE (with different PT but within same category) from 6th to 11th January and same AE from 10th to 12th January, these will be collapsed into one clustered AE from 1st to 12th January. [Table 4](#) is summarizing key derivation steps for each type of clustered AEs.

Time-to resolution of AE (any grade) for a specific category is defined as the longest time from onset to complete resolution or improvement to the grade at baseline among all clustered select AEs in this category experienced by the subject. Events which worsened into grade 5 events (death) or have a resolution date equal to the date of death are considered unresolved. If a clustered AE is considered as unresolved, the resolution date will be censored to the last known date alive. Improvement to the grade at baseline implies that all different adverse events in the clustered adverse event should at least have improved to the corresponding (i.e. with same

preferred term) baseline grade. This measure is defined only for subjects who experienced at least one AE in the specific category.

The time-to resolution of AE (grade 3-5) for a specific category is defined similarly with an onset date corresponding to a grade 3-5 AE.

Time-to resolution of drug-related AE (any grade or grade 3-5) is defined similarly but restricted to drug-related AE.

The time-to resolution of AE (any grade or grade 3-5, drug-related or all) where immune modulating medication was initiated is defined similarly with the additional condition that the subject started an immune modulating medication during the longest AE resolution period.

Time-to resolution for a specific subcategory is defined similarly but restricted to event of this subcategory.

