### **7.6.8.3 Time-to resolution of IMAE**

Time to resolution of the following specific events will be summarized separately for each category/subcategory.

- Time-to resolution of any grade IMAE
- Time-to resolution of grade 3 to 5 IMAE

Time-to resolution analyses are restricted to treated subjects who experienced the specific events. Time-to resolution where immune modulating medication was initiated analyses is restricted to treated subjects who experienced the specific events and who received immune modulating medication during the longest IMAE.

The following summary statistics will be reported: percentage of subjects who experienced the specific events, percentage of subjects with resolution of the longest IMAE, median time-to resolution along with 95% CI (derived from Kaplan-Meier estimation) and ranges.

See time-to resolution definition subsection of [Appendix 1](#) for additional details.

The analyses will be conducted using the 100-day safety window.

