**Table 4: Derivation of clustered AE of interest**

Type of clustered AE of interest	Derivation
Any grade	Collapse any on-treatment AE from the same category
Drug-related of any grade	Collapse any on-treatment drug-related AE from the same category
Grade 3-5	Collapse any on-treatment AE from the same category. Resolution will be based on the onset date of the earliest grade 3-5 records (if no grade 3-5 record, clustered AE is excluded)
Drug-related of Grade 3-5	Collapse any on-treatment drug-related AE from the same category Resolution will be based on the onset date of the earliest grade 3-5 record (if no Grade 3-5 record, clustered AE is excluded)

The algorithm for collapsing adverse event of interest (IMAE, select AE, other event of special interest) records is using the following conventions:

For each subject and specified category, the corresponding adverse event records will be collapsed when:

- 1) Multiple adverse event records have the same onset date.
- 2) The onset date of an event record is either the same day or 1 day later than the resolution date of a preceding event record (contiguous events).

The onset date of an event record is after the onset date and prior to or on the resolution date of a preceding event record (overlapping events).

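### Resolution status comes from the longest clustered event only, so a shorter, separate fatal or unresolved Grade 3-5 IMAE in the same category can leave the subject counted as resolved

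*SAP*

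**What the plan says.** SAP Appendix 1 (Time-to resolution definition) first collapses overlapping or contiguous events within a category into clusters. Time to resolution is then "defined as the longest time from onset to complete resolution or improvement to the grade at baseline among all clustered select AEs", so each subject contributes one value per category.

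The sentence names select AEs, but the rule also governs IMAEs. The opening of Appendix 1 and the collapsing algorithm under Table 4 both list them, and SAP 7.6.8.3 sends the reader there ("See time-to resolution definition subsection of" Appendix 1). The Grade 3-5 version follows the same rule, with the clock starting at the earliest Grade 3-5 record in the cluster; "if no grade 3-5 record, clustered AE is excluded".

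Three further provisions matter:

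- On deaths: "Events which worsened into grade 5 events (death) or have a resolution date equal to the date of death are considered unresolved". For any unresolved cluster, "the resolution date will be censored to the last known date alive".
- SAP 7.6.8.3 reports the "percentage of subjects with resolution of the longest IMAE".
- Events merge when one starts "either the same day or 1 day later than the resolution date of a preceding event record", or when they overlap.

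SAP 7.6.2 describes time to resolution more simply, from onset to end date. It does not say which event is used when a subject has several. Nothing in the visible text gives a fatal or unresolved cluster precedence over a longer one that resolved.

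**The concern.** Length and outcome are separate facts, and the plan uses the first to choose the second. An unresolved cluster is measured only up to the last known alive date, so a rapidly fatal one has a short observed length. If the same subject had an earlier, longer cluster in that category that resolved, the longest-cluster rule selects the earlier one. The subject then enters both the Kaplan-Meier estimate and the percentage as resolved, although Appendix 1 classes the fatal event as unresolved.

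The SAP's secondary objective (Section 3.2) is to describe the outcome of all high-grade IMAEs. In the visible text, the longest-IMAE percentage in 7.6.8.3 is the only IMAE resolution percentage that is defined. Choosing by length can raise that percentage relative to counting every cluster, and can never lower it.

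**Working it through.** **Inputs.** From SAP Appendix 1 and Table 4: the merging rule, the longest-cluster rule, the unresolved status of fatal events, and censoring at the last known alive date. From SAP Section 8: duration = last date − first date + 1. From Protocol 8.1: a 13% planning rate and 150 subjects. All event dates and recurrence figures below are assumptions, because the documents give none.

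**1. The SAP's own example.** The records run 1-5, 6-11 and 10-12 January. Merge when onset ≤ previous end + 1: 6 ≤ 5 + 1 and 10 ≤ 11 + 1, so all three join. The SAP states the same result: "these will be collapsed into one clustered AE from 1st to 12th January".

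**2. Two separate clusters.** Assume a Grade 3 IMAE on days 1-60 that resolved (60 − 1 + 1 = 60 days), then a same-category Grade 3-5 event starting on day 90. Since 90 > 60 + 1, they do not merge.

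| Second cluster | Its observed length | Value the SAP analyses |
|---|---|---|
| Fatal | 5, 20 or 59 days | 60 days, resolved |
| Fatal | 61 days | 61 days, censored |
| Fatal | 80 days | 80 days, censored |
| Grade 3, open at last contact on day 119 | 119 − 90 + 1 = 30 days | 60 days, resolved |

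If the fatal event instead runs from day 61 to day 80, the two merge into one 80-day censored cluster and nothing is masked.

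**3. Does the reading matter?** If the longest time is taken only over clusters that resolved, the short unresolved cluster still drops out. The result is the same.

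**4. Scale.** Expected subjects with a Grade 3-5 IMAE: 0.13 × 150 = 19.5, about 20 over the ten categories in Protocol Table 6.2.2-1. If h of N affected subjects in a category are masked and all others resolved, the SAP reports 100%, and the share with every cluster resolved is (N − h)/N. For N = 10, h = 1 this is 9/10 = 90%. For N = 20, h = 1 it is 19/20 = 95%.

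**5. How often the unresolved cluster is the shorter one.** Assume exponential lengths, with mean 8 weeks for the resolved cluster and mean m weeks for the unresolved one. The masked share is 8/(8 + m):

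- m = 4: 8/12 = 67%
- m = 8: 8/16 = 50%
- m = 26: 8/34 = 24%
- m = 52: 8/60 = 13%

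The overstatement of percent resolved is (share with a second cluster) × (share of those unresolved) × (masked share). Taking 10-30% and 20-30% for the first two:

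- m = 4: 0.1 × 0.2 × 0.67 = 1.3 points to 0.3 × 0.3 × 0.67 = 6.0 points
- m = 52: 0.1 × 0.2 × 0.13 = 0.3 points to 0.3 × 0.3 × 0.13 = 1.2 points

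**6. Would timing the fatal cluster instead help?** Take 17 invented subjects resolving at 10, 14, 18, 21, 25, 28, 32, 35, 40, 45, 50, 55, 60, 66, 72, 80 and 90 days, plus three masked subjects. Entered as resolved at 60 days, the Kaplan-Meier median is 45 days. Entered as censored at 20 days, it is 40 days, so resolution looks faster. The correction therefore belongs in the percentage resolved, not in the choice of which cluster to time.

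**The case against.** **Ongoing events in survivors are mostly safe.** A reader might infer that any event still open at analysis is masked. The documents do not support that. Unresolved clusters are censored at the last known alive date, survival is collected every 3 months for 5 years (Protocol Table 5.1-3), and the final analysis follows that period (SAP Schedule of Analyses). At that point an open event in a survivor has usually run for months or years and tends to be the longest, so the rule selects it. What remains are fatal events, and events open at an early death, a loss to follow-up or one of the interim publication cuts. This part of the objection stands.

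**The size cannot be claimed.** A reader might also infer that half or more of unresolved second clusters are masked. Step 5 gives that only for an assumed mean of 4 to 8 weeks; at 26 or 52 weeks the share is 24% or 13%. The documents supply neither these lengths nor a recurrence rate.

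**Masking needs an unusual pattern.** It takes two non-contiguous clusters in one category, in one subject, each with a Grade 3-5 record and within the 100-day window. The permanent-discontinuation criteria in Protocol 4.5.4.1 make many repeat events on drug less likely. This stands as a limit on frequency.

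**Fatal IMAEs are not lost from the report.** They count in the primary analysis (SAP 7.6.1), in the Grade 5 column and by-subject listing (7.6.8.1), and in the deaths section (7.6.3). The label in 7.6.8.3 also says openly that it concerns the longest event. Both points are correct, but neither display corrects the resolution percentage.

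**Longest duration is a cautious summary.** It does lengthen the reported toxicity, and choosing the first or the longest cluster for timing is a matter of preference. That defends the duration measure. It does not defend using the longest event to decide whether the subject resolved.

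**Conclusion.** The point holds in a limited form. Followed exactly, the plan counts a subject as resolved when a shorter, separate Grade 3-5 cluster in the same category was fatal, or was unresolved at an early death, loss to follow-up or interim cut. That conflicts with Appendix 1's own classification of fatal events and with an objective covering all high-grade IMAEs, and the error can only flatter the percentage.

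The frequency cannot be derived from the documents and is probably small, given about 20 subjects with high-grade IMAEs spread over ten categories. Small denominators still make a single case visible: 90% becomes 100% in the assumed category of 10. The conclusion rests on the visible text. The Data Presentation Plan and the Core Safety SAP, which the SAP cites, are not among the documents reviewed.

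**What to change.** In SAP 7.6.8.3 and Appendix 1:

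- Report, by category, the percentage of subjects in whom every Grade 3-5 cluster resolved. Any fatal or unresolved Grade 3-5 cluster makes the subject unresolved.
- Beside it, give the number of subjects with any fatal or unresolved Grade 3-5 cluster.
- Keep the longest-cluster time to resolution, labelled as a worst-duration summary.
- State how that summary relates to the onset-to-end-date definition in SAP 7.6.2, so that the two passages agree on which event is used when a subject has several.

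The cost is SAP wording and a small derivation change on data already collected. Percent resolved may come out slightly less favourable.

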##### 4.2 Secondary Endpoint(s)

The secondary objective of the study will be assessed by measuring the following:

- median time to onset, median time to resolution of high grade (Grade 3-4 and Grade 5) IMAEs
- percentage of subjects who received immune modulating medication (e.g. corticosteroids, infliximab, cyclophosphamide, Intravenous Immune Globulin [IVIG], and mycophenolate mofetil), or hormonal replacement therapy, the percentage of subjects who received  $\geq 40$  mg prednisone equivalents, total duration of all immune modulating medications given for the IMAE and summary of subjects with resolution of AEs after initiating these therapies.

█ [REDACTED]

█ [REDACTED]

█ [REDACTED]

█ [REDACTED]

[REDACTED]

[REDACTED]

[REDACTED]

[REDACTED]

[REDACTED]

[REDACTED]

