### **7.6.2 Secondary Analyses**

Additional descriptive statistics will include median values using the Kaplan-Meier (KM) product-limit method with 95% CI using Brookmeyer and Crowley of time to onset and time to resolution of IMAEs, and will be presented for all treated subjects in Groups 1, 2, and 3. Time to onset is calculated from first dosing date to the event onset date. If a subject never experienced the given AE, the subject will be censored at the last contact date. Time to resolution is calculated from the AE onset date to AE end date. If an AE is ongoing at the time of analysis, the time to resolution will be censored at the last contact date.

Management of high-grade (CTCAE v4.0 Grade 3-4 and Grade 5) IMAEs will be characterized by measuring percentage of subjects who received immune modulating medication (or hormonal replacement therapy), percentage of subjects who received  $\geq 40$  mg prednisone equivalents, and total duration of all immune modulating medications given for the event, in all treated subjects who have experience high-grade (CTCAE v4.0 Grade 3-4 and Grade 5) IMAEs and all subjects in Groups 1, 2, and 3.

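### The Kaplan-Meier median time to resolution of IMAEs censors subjects who die unresolved, although death is a competing event, and this biases the median toward shorter times

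*SAP*

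**What the plan says.** SAP 4.2 names as a secondary endpoint the "median time to onset, median time to resolution of high grade (Grade 3-4 and Grade 5) IMAEs". Protocol 8.3.2 words the same endpoint for Grade 3-4 only. The analysis paragraph of the protocol synopsis includes Grade 5, and SAP 7.6.8.3 analyses any-grade and Grade 3 to 5 events.

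The rules that build the time variable are:

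- **Who is analysed** (SAP 7.6.8.3): "Time-to resolution analyses are restricted to treated subjects who experienced the specific events".
- **How death is classed** (SAP Appendix 1, time-to resolution definition): "Events which worsened into grade 5 events (death) or have a resolution date equal to the date of death are considered unresolved".
- **What happens to unresolved events** (same place): "If a clustered AE is considered as unresolved, the resolution date will be censored to the last known date alive".
- **What is reported** (SAP 7.6.8.3): among other items, the "percentage of subjects with resolution of the longest IMAE" and the "median time-to resolution along with 95% CI (derived from Kaplan-Meier estimation) and ranges".

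SAP 7.6.2 also plans a Kaplan-Meier median for time to resolution. Its only censoring rule is: "If an AE is ongoing at the time of analysis, the time to resolution will be censored at the last contact date". It has no separate rule for subjects who die. The readable text of the SAP contains no competing-risk estimate and no sensitivity analysis for death.

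**The concern.** Kaplan-Meier lets a censored subject stand for someone who would have gone on resolving at the same rate as those still under observation. That is reasonable for a subject whose event is ongoing at the data cut. It is not reasonable for a subject who has died. The SAP handles both in the same way.

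Two kinds of subject are affected. One has an IMAE that becomes fatal. The other dies of any other cause, including the cancer, while an IMAE is still open. In a population with advanced or metastatic disease the second kind cannot be assumed rare.

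The secondary objective is to characterise the outcome of high-grade IMAEs. A median that treats death with an open event as ordinary loss of follow-up errs in the favourable direction, because it makes these events look shorter-lived than they were.

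**Working it through.** The documents state no figure for time to resolution, so there is none to reproduce. The check is of direction and then of size.

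**Inputs from the documents.** Protocol 8.1 assumes a Grade 3-5 IMAE rate of 13% among 150 subjects: 0.13 × 150 = 19.5, or about 20 subjects overall, and fewer in each IMAE category.

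**Inputs assumed.** Constant hazards, and a share q of affected subjects who die unresolved. The documents give neither, so q is taken as a range.

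**1. Direction.** At each resolution, 1 − Kaplan-Meier rises by S(t−)/Y(t), where Y is the number at risk and S falls only at resolutions. The Aalen-Johansen curve rises by S₀(t−)/Y(t), where S₀ falls at deaths as well. Since S₀ ≤ S, 1 − Kaplan-Meier is never below Aalen-Johansen, and it is strictly above once a death is followed by a resolution. The Kaplan-Meier median is therefore never the longer of the two.

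**2. Fixed example.** Take 20 subjects with one event on each of days 1 to 20.

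| Days of death | Final resolved, KM | Final resolved, AJ | Median, KM | Median, AJ |
|---|---|---|---|---|
| 3, 9 | 100% | 90% | 12 | 12 |
| 3, 6, 9, 12 | 100% | 80% | 13 | 14 |
| 3, 5, 8, 10, 13, 15 | 100% | 70% | 14 | 16 |
| 17, 18, 19, 20 | 80% | 80% | 10 | 10 |

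The last row shows no effect when all deaths follow the last resolution. The first row shows that with few deaths the median may not move in a small sample.

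**3. Size under constant hazards.** Let p = 1 − q be the share that resolves before death and r the resolution hazard. The total hazard is r/p.

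- Kaplan-Meier median: ln 2 / r.
- Cumulative incidence: p[1 − exp(−rt/p)]. Setting this to 0.5 gives t = p[−ln(1 − 0.5/p)]/r.
- Ratio of medians: p[−ln(1 − 0.5/p)]/ln 2.

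| q | p | p[−ln(1 − 0.5/p)] | Ratio | If the KM median is 8.0 weeks (assumed) |
|---|---|---|---|---|
| 10% | 0.9 | 0.730 | 1.05 | 8.4 weeks |
| 20% | 0.8 | 0.785 | 1.13 | 9.1 weeks |
| 30% | 0.7 | 0.877 | 1.27 | 10.1 weeks |
| 40% | 0.6 | 1.075 | 1.55 | 12.4 weeks |

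At q = 50% the cumulative incidence only approaches 50%, and above that it stays below, so the competing-risk median is not reached. Kaplan-Meier would still report one.

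**4. With 20 subjects.** In 4,000 simulated samples under the same assumptions, the typical Kaplan-Meier and competing-risk medians were 7.69 and 7.77 weeks with 2 deaths expected, 7.97 and 8.45 with 4, and 7.98 and 9.03 with 6. In the last case 1.6% of samples did not reach the competing-risk median and are left out of its figure. The shift has the same direction as in step 3 and is smaller.

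**5. Would censoring deaths at maximum follow-up do instead?** Let the death hazard be d and the hazard of other censoring be c. If deaths stay in the risk set indefinitely, the large-sample final resolved proportion is 1 − [d/(r+d+c)]^(r/(r+c)). Take r = 1 and d = 0.25, so the true proportion is 80%.

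- c = 0: 1 − 0.2 = 80%.
- c = 0.25: 1 − (1/6)^0.8 = 76%.
- c = 0.5: 1 − (1/7)^(2/3) = 73%.

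It agrees with Aalen-Johansen only when nobody else is censored earlier. Otherwise it errs the other way.

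**The case against.** The strongest case against has four parts.

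**The resolved proportion is sound.** A reader might infer that the plan will overstate how many subjects recover. The documents do not support that. The proportion planned in SAP 7.6.8.3 is a crude percentage, and Appendix 1 already counts deaths as not resolved. The readable text plans no Kaplan-Meier resolved proportion. Fatal IMAEs are also visible elsewhere: SAP 7.6.8.1 gives Grade 5 its own column, and deaths are analysed separately. This stands, and it confines the point to the median. The crude percentage does not correct the median.

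**The size is assumed.** No document gives the share dying unresolved, and the larger shifts need 30% to 40%. At 10%, with about 18 resolutions, an exponential 95% interval for the median runs from exp(−1.96/√18) = 0.63 to exp(1.96/√18) = 1.59 times the estimate, far wider than a 5% shift. This stands too. Still, sampling error is shown in the interval, whereas this bias is not shown and always has the same sign.

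**The onset rule is no precedent.** SAP Appendix 1 says that for subjects without an event "time-to onset will be censored at the maximum follow-up time of all subjects in their respective treatment group". A reader might infer that the SAP contradicts itself and already holds the remedy. Onset in all treated subjects and duration in affected subjects are different quantities, so different censoring is not in itself a contradiction. SAP 7.6.2 moreover censors onset at last contact, so the onset rule is itself unsettled. Step 5 of the working shows that the maximum follow-up rule is not a safe substitute.

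**It is a choice of estimand.** The death-censored median describes the resolution rate among subjects still alive. That is a legitimate quantity, but the SAP does not say it is the target, and a reader of a median time to resolution will take it as the time by which half of affected subjects had resolved.

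**Conclusion.** The point holds for the Kaplan-Meier median time to resolution and for nothing beyond it. Followed exactly, the SAP treats death with an open IMAE as uninformative censoring, and this can only shorten the median. The direction is certain. The size is not: about 5% at 10% dying unresolved, rising to 13%, 27% and 55% at 20%, 30% and 40%, all under assumed constant hazards. It is zero if every death follows the last resolution, and the median does not move if deaths fall only after it has been reached.

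The primary incidence endpoint and the crude percentage resolved are untouched. This is a descriptive secondary endpoint in a single-arm study with about 20 high-grade cases expected. The correction is worth making because it is cheap and the error favours the drug, not because a large distortion has been shown.

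The grade range matters to the result. Limiting the endpoint to Grade 3-4, as in protocol 8.3.2, could take fatal IMAEs out, whereas SAP 4.2 puts them in. Deaths from other causes with a Grade 3-4 IMAE still open would remain under either wording.

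**What to change.** In SAP 7.6.2, 7.6.8.3 and Appendix 1:

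- For the any-grade and Grade 3-5 IMAE analyses, estimate the cumulative incidence of resolution by Aalen-Johansen, with death before resolution as a competing event. Censor only subjects alive with an ongoing event.
- Take the median from that curve, and state it as not reached if the curve stays below 50%.
- Report the number of subjects who died with the event unresolved, overall and by category.
- If wanted, keep the death-censored Kaplan-Meier median as a secondary description, labelled as such.
- Do not offer censoring of deaths at maximum follow-up as an equivalent.
- Use one censoring date for ongoing events. SAP 7.6.2 says last contact and Appendix 1 says last known alive.

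Reconcile the grade range of the endpoint between protocol 8.3.2 and SAP 4.2, and state whether fatal IMAEs are in the analysis.

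The analysis needs no data beyond the dates of death, AE onset and AE resolution that the SAP already uses. The cost is revised wording, a little more analysis work, and medians that may be slightly longer or not reached.
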